
1.0 BACKGROUND AND JUSTIFICATION

1.1 Cyclin Dependent Kinases

1.2 Cell Cycle Inhibition in Pancreatic Cancer

The activity of CDK4/6 is frequently deregulated in pancreatic cancer due to the loss of *CDKN2A* via either homozygous deletion or epigenetic silencing. The signature driver of pancreatic cancer (*KRAS*) drives cells into senescence through activation of *CDKN2A*. Thus, there is a potent hypothetical rationale for pharmaceutically mimicking the function of *CDKN2A* based on a plethora of published data. Most recently, in the sequencing of over 109 cases, we discovered amplification of *CCND1* and *CDK4* also occurs in pancreatic adenocarcinoma (Figure 2), while the loss of *RB* is rare⁽⁸⁾. Therefore from a genetic perspective one would anticipate that pancreatic cancers could respond efficiently to CDK4/6 inhibition.

[figure not shown]

Figure 3. The RB-pathway in Pancreatic Cancer. 109 dissected pancreatic cancers were subjected to whole exome sequencing. Frequent loss of *CDKN2A/2B* was observed, and amplification of *CCND1* and *CDK4* was found in select cases. *RB1* loss that compromises the action of CDK4/6 inhibitors was observed in ~3% of cases. (Blue boxes denote homozygous deletion, green boxes denote mutation, and red boxes denote amplification). Data and figure from Witkiewicz, et al.⁽⁸⁾

In patient-derived patient derived xenografts we found that CDK4/6 inhibition was highly effective at limiting tumor growth, and had a profound impact on proliferative index (Figures 3 and 4). This finding was also recapitulated in the analysis of primary tumor explants (Figures 5 and 6). Both of these patient-derived models recapitulate the histology and tumor microenvironment of pancreatic cancer. Interestingly, we did identify a single case (out of 15 tested) that failed to response to CDK4/6 inhibition. We could show that the basis for the lack of response is loss of *RB*; therefore select biomarkers can be deployed to define rare tumors which fail to respond (Figure 6). Overall, these data suggest that the vast majority of primary pancreatic cancers would have the capacity to response to CDK4/6 inhibition.

[figure not shown]

Figure 4. Potent Impact of CDK4/6 Inhibition in Patient-derived Xenografts: (A) Three patient derived xenograft models were employed that maintained the tissue architecture consistent with the primary tumor. (B) Xenograft models were treated with CDK4/6 inhibitor by oral gavage daily. Tumor volume was determined by daily measuring and lead to a substantial impact on tumor size.

[figure not shown]

Figure 5. Potent Impact of CDK4/6 Inhibition in Patient-derived Xenografts: Xenograft models were treated with CDK4/6 inhibitor by oral gavage daily. At sacrifice tissue were stained with Ki67. Data show significant cytostatic activity across the models employed.

[figure not shown]

Figure 6. Schematic of the Explant Approach: Surgical tissue is cultured *ex vivo* and treated with specific drugs. Samples are processed and stained for specific markers. In this fashion the model recapitulates serial biopsying of primary tumor during treatment.

[figure not shown]

Figure 7. Response of 15 cases to CDK4/6 Inhibition: (A) Surgical tissues from 15 different patients were exposed *ex vivo* to CDK4/6 inhibition and impact on Ki67 was determined. >95% of cases could respond. (B) Staining for RB and p16ink4a demonstrated that the vast majority of cases have low p16ink4a levels and robust nuclear RB staining. The one case that failed to respond had very high p16ink4a and loss of nuclear RB in the tumor compartment.

In the context of this clinical trial the disease will be advanced and perhaps more indicative of aggressive models of disease. In evaluation of such models, our group and others found that while some models respond very effectively, others can develop resistance to CDK4/6 inhibition in spite of loss of *CDKN2A* (Figure 7). We explored the mechanism and found that there is deregulation of parallel pathways that facilitate the bypass which involves signaling to other CDK/Cyclins and involves the mTOR pathway^(9, 10). In drug screening, our group and others found that mTOR inhibitors were particularly potent cooperative agents with CDK4/6 inhibitors across all models^(9, 10) and served to broaden the efficacy of CDK4/6 inhibition into resistant models (Figure 8).

[figure not shown]

Figure 8. Established Pancreatic Lines have Limited Response to CDK4/6 Inhibition: Bromodeoxyuridine (BrdU) incorporation was determined in the presence of CDK4/6 inhibition, demonstrating substantial residual cell cycle progression. These cells were further able to proliferate in spite of treatment as determined by crystal violet staining.

[figure not shown]

Figure 9. MTOR Inhibitors are Synergistic with CDK4/6 Inhibition in Pancreatic Cancer Models.

Treatment with CDK4/6 inhibitors can lead to an accumulation or maintenance of mTOR activity as measured by phosphorylated S6 kinase. While phosphatidylinositol 3-kinase (PI3K) inhibitors have modest effects, mTOR inhibitors are synergistic for the suppression of proliferation and lead to active cell killing. In contrast, MEK inhibitors suppress proliferation but do not induce apoptosis in these models. Identical results were observed by independent groups using different cell lines and xenograft models^(9, 10).

Together the genetic rationale, the findings in patient-derived models, and aggressive established models of metastatic disease suggest that CDK4/6 inhibitors in combination with mTOR inhibitors can have a highly significant impact on a broad range of pancreatic cancers. The use of combination approaches is particularly important since resistance to CDK4/6 inhibition as a single agent can develop in pancreatic adenocarcinoma models, and by all accounts mTOR inhibitors are particularly effective at countering the acquisition of resistance and actively leading to the death of cell treated with CDK4/6 inhibitors^(9, 10).

1.3 LEE011 (Investigator's Brochure⁽²⁴⁾)

[REDACTED]

[REDACTED]

[REDACTED]

[REDACTED]

[REDACTED]

[REDACTED]

[REDACTED]

[REDACTED]

[REDACTED]

[REDACTED]

[REDACTED]

[REDACTED]

[REDACTED]

[REDACTED]

[REDACTED]

[figure not shown]

[figure not shown]

[figure not shown]
[figure not shown]

[figure not shown]
[figure not shown]

[figure not shown]
[figure not shown]

[figure not shown]
[figure not shown]
[figure not shown]
[figure not shown]
[figure not shown]

[figure not shown]

[figure not shown]
[figure not shown]
[figure not shown]
[figure not shown]

[figure not shown]
[figure not shown]

[figure not shown]
[figure not shown]

[figure not shown]
[figure not shown]

[figure not shown]
[figure not shown]

[figure not shown]
[figure not shown]
[figure not shown]
[figure not shown]
[figure not shown]
[figure not shown]
[figure not shown]

[figure not shown]

[figure not shown]
[figure not shown]
[figure not shown]
[figure not shown]
[figure not shown]
[figure not shown]
[figure not shown]
[figure not shown]

[figure not shown]

[figure not shown]
[figure not shown]
[figure not shown]
[figure not shown]
[figure not shown]

[figure not shown]

[figure not shown]

[figure not shown]
[figure not shown]

[figure not shown]
[figure not shown]
[figure not shown]
[figure not shown]
[figure not shown]
[figure not shown]
[figure not shown]
[figure not shown]

[figure not shown]

[figure not shown]
[figure not shown]
[figure not shown]
[figure not shown]
[figure not shown]
[figure not shown]
[figure not shown]
[figure not shown]
[REDACTED]

[figure not shown]

[figure not shown]

[figure not shown]

[figure not shown]

[figure not shown]

[figure not shown]

[figure not shown]

[figure not shown]

[figure not shown]

[REDACTED]

[REDACTED]

[REDACTED]

1 2 3 4 5 6 7 8 9 10 11 12 13 14 15 16 17 18 19 20 21 22 23 24 25 26 27 28 29 30 31 32 33 34 35 36 37 38 39 40 41 42 43 44 45 46 47 48 49 50 51 52 53 54 55 56 57 58 59 60 61 62 63 64 65 66 67 68 69 70 71 72 73 74 75 76 77 78 79 80 81 82 83 84 85 86 87 88 89 90 91 92 93 94 95 96 97 98 99 100

[figure not shown]
											
											
											
											
											
											
											
											
											
											
											
											
											

1.4 Everolimus (Afinitor® Package Insert⁽²⁹⁾)

1.4.1 Chemical Structure of Everolimus

Everolimus is an inhibitor of mammalian target of rapamycin (mTOR), a serine-threonine kinase downstream of the phosphoinositide 3-kinase (PI3K)/AKT pathway. Its chemical name is (1R,9S,12S,15R,16E,18R,19R,21R,23S,24E,26E,28E,30S,32S,35R)-1,18-dihydroxy-12-[(1R)-2-[(1S,3R,4R)-4-(2-hydroxyethoxy)-3-methoxycyclohexyl]-1-methylethyl]-19,30-dimethoxy-15,17,21,23,29,35-hexamethyl-11,36-dioxo-4-aza-tricyclo[30.3.1.0^{4,9}]hexatriaconta-16,24,26,28-tetraene-2,3,10,14,20-pentaone. The molecular formula is C₅₃H₈₃NO₁₄ and the molecular weight is 958.2 grams per mole. The tablets also contain anhydrous lactose, butylated hydroxytoluene, crospovidone, hypromellose, lactose monohydrate, and magnesium stearate as inactive ingredients.

Figure 11: Molecular Structure of Everolimus

1.4.2 Everolimus Mechanism of Action

Everolimus inhibits mTOR kinase activity by binding to FKBP-12 intracellularly forming a complex with mTOR complex 1 (mTORC1). This inhibition has been demonstrated to decrease cell proliferation and angiogenesis through decreased expression of hypoxia-inducible factor 1 (HIF-1) and vascular endothelial growth factor (VEGF). It also reduces protein synthesis by decreasing activity of S6 ribosomal protein kinase (S6K1) and eukaryotic initiation factor 4E-binding protein 1 (4E-BP1).

1.4.3 Everolimus Pharmacokinetics

Peak serum concentrations are observed within 1-2 hours and are proportional to dosing between 5 and 10 mg daily. Above 20 mg the maximum concentration is less than dose-proportional, but the AUC demonstrates a maintenance of dose-proportionality up to 70 mg. Steady-state concentration is reached in 2 weeks. Fatty meals may reduce serum concentrations, and it is recommended that patients take the medication consistently either with or without food. Blood-to-plasma ratio is 17-73%, with about 20% confined to plasma, and 74% plasma protein binding.

Everolimus is a potent competitive inhibitor of CYP3A4, a mixed inhibitor of CYP2D6, and a substrate of PgP. Thus, avoidance of co-administration with strong CYP3A4/PgP inhibitors and dose-reduction with moderate CYP3A4/PgP inhibitors is recommended. 80% of the drug is excreted in the feces and 5% in the urine, with a mean half-life of elimination of about 30 hours. Clearance of everolimus does not vary based on creatinine clearance (as low as 25 mL/min) and no dose adjustment is recommended; however, no clinical studies were conducted in patients with decreased renal function. There are notable increases in serum concentration of everolimus in patients with impaired liver function, with relative increases in AUC by 1.8-, 3.2-, and 3.6-fold in patients with Child-Pugh classes A, B, and C respectively. Recommended dose adjustments include decreasing to 7.5 mg daily, 5 mg daily, and 2.5 mg daily in Child-Pugh classes A, B, and C respectively, with further dose reductions for tolerability. Use in Child-Pugh class C is only recommended if the benefits outweigh the risks of administration.

QTc prolongation was not seen in a trial of 59 healthy subjects given doses up to 50 mg in a single dose, and carcinogenesis was not observed in animal studies. Animal studies do suggest that everolimus may impair male and female fertility.

After administration of AFINITOR tablets in patients with advanced solid tumors, peak everolimus concentrations are reached 1 to 2 hours after administration of oral doses ranging from 5 mg to

70 mg. Following single doses, C_{max} is dose-proportional with daily dosing between 5 mg and 10 mg. With single doses of 20 mg and higher, the increase in C_{max} is less than dose-proportional, however AUC shows dose-proportionality over the 5 mg to 70 mg dose range. Steady-state was achieved within 2 weeks following once-daily dosing.

The blood-to-plasma ratio of everolimus, which is concentration-dependent over the range of 5 to 5000 ng/mL, is 17% to 73%. The amount of everolimus confined to the plasma is approximately 20% at blood concentrations observed in cancer patients given everolimus 10 mg/day. Plasma protein binding is approximately 74% both in healthy subjects and in patients with moderate hepatic impairment.

Everolimus is a substrate of CYP3A4 and PgP. Following oral administration, everolimus is the main circulating component in human blood. Six main metabolites of everolimus have been detected in human blood, including three monohydroxylated metabolites, two hydrolytic ring-opened products, and a phosphatidylcholine conjugate of everolimus. These metabolites were also identified in animal species used in toxicity studies, and showed approximately 100-times less activity than everolimus itself.

In vitro, everolimus competitively inhibited the metabolism of CYP3A4 and was a mixed inhibitor of the CYP2D6 substrate dextromethorphan.

No specific elimination studies have been undertaken in cancer patients. Following the administration of a 3 mg single dose of radiolabeled everolimus in patients who were receiving cyclosporine, 80% of the radioactivity was recovered from the feces, while 5% was excreted in the urine. The parent substance was not detected in urine or feces. The mean elimination half-life of everolimus is approximately 30 hours.

1.4.4 Everolimus Drug Approval

Everolimus (Afinitor®) is currently approved by the Food and Drug Administration (FDA) for multiple indications: postmenopausal advanced hormone-receptor positive, HER2-negative breast cancer in combination with exemestane after failure with letrozole or anastrozole, pancreatic neuroendocrine tumors (PNET) that are unresectable, locally advanced, or metastatic, advanced renal cell carcinoma (RCC) after failure with sunitinib or sorafenib, renal angiomyolipoma and tuberous sclerosis complex (TSC) not requiring immediate surgery, and TSC with subependymal giant cell astrocytoma (SEGA) that is unresectable. Everolimus (Zortress®) is also approved for organ rejection prophylaxis in kidney and liver transplant patients.

1.5 Pancreatic Cancer

Cancer of the pancreas is the fourth leading cause of cancer death in the United States, with an estimated 48,960 new diagnoses and 40,560 deaths attributable to the disease in 2015⁽³⁰⁾. Presently, surgical resection offers the only chance of cure. However only 15 to 20 percent of patients have resectable disease at initial diagnosis; the majority have either locally advanced or metastatic cancer. Of those who are surgical candidates, most will have disease relapse after curative surgery. Reported five-year survival rates following pancreaticoduodenectomy for node-negative and node-positive disease are 25 to 30, and 10 percent, respectively^(31, 32). For those who are unresectable at diagnosis, the outcomes are even poorer. Median survival is 12-15 months for patients with locally advanced unresectable disease, and only 8-11 months for those who present with metastases^(2-4, 33-36). Thus, better medical intervention is desperately needed.

1.5.1 First Line Therapy in Pancreatic Cancer

Only recently have there been improvements in systemic therapy for advanced pancreatic cancer. Originally, gemcitabine became the standard front line therapy after a head to head comparison

with 5-fluorouracil (5-FU) showed gemcitabine to be superior⁽²⁾. Gemcitabine and 5-FU were found to yield an 18 percent versus 2 percent one-year survival and a 24 percent versus 4.8 percent improvement in clinical benefit response, respectively. For over 10 years, no clinically meaningful improvement in survival was achieved for any regimen compared to gemcitabine alone. Finally in 2011, the combination of 5-FU, oxaliplatin, and irinotecan (FOLFIRINOX) was compared against gemcitabine in a phase III trial with promising results, and FOLFIRINOX is considered the standard first-line treatment option in patients with a good performance status (PS 0-1)⁽³⁾. The median overall survival (mOS) was 11.1 months in the FOLFIRINOX group as compared with 6.8 months in the gemcitabine group. The mPFS was 6.4 months in the FOLFIRINOX group as compared with 3.3 months in the gemcitabine group. The objective response rate was 31.6% in the FOLFIRINOX group versus 9.4% in the gemcitabine group ($P<0.001$). More adverse events were noted in the FOLFIRINOX group including 5.4% of patients in this group who had febrile neutropenia. More recently, in a 2013 Phase III trial, the combination of gemcitabine and *nab*-paclitaxel was also demonstrated to be superior over gemcitabine alone⁽⁴⁾. The median overall survival of gemcitabine and *nab*-paclitaxel was 8.5 months, which was statistically superior to the 6.7 month survival seen with single agent gemcitabine. The mPFS was 5.5 months in the gemcitabine plus *nab*-paclitaxel group as compared with 3.7 months in the gemcitabine group. The objective response rate was 23% in the gemcitabine plus *nab*-paclitaxel group versus 7% in the gemcitabine group ($P<0.001$). More adverse events were noted in the gemcitabine plus *nab*-paclitaxel group including 3% of patients in this group who had febrile neutropenia. This trial has effectively established gemcitabine plus *nab*-paclitaxel as another definitive first-line treatment option for patients with metastatic pancreatic cancer. These two trials now form the standard for comparison for first line treatment for metastatic pancreatic cancer, and it should be noted that, based on these data, patients on the study proposed herein who are receiving first line therapy will be expected to remain on first line therapy for an average of ~6 months.

1.5.2 Second Line Therapy in Pancreatic Cancer

Research into second line therapy for pancreatic cancers is yet to reveal an obvious choice that shows efficacy above and beyond its comparators. Second line trials have demonstrated response rates of 2.5 to 24% and mOS rates of 4 to 6 months⁽³⁷⁻⁵⁵⁾. The best mOS rate from combination therapy for second line treatment is typically around six months (range 3-9 months). Promising data came from the results of the CONKO-003 trial⁽³⁷⁾. Patients who had progressed on gemcitabine were randomized to 5-FU plus oxaliplatin vs. best supportive care (which could include 5-FU alone). Patients treated with a combination of 5-FU and oxaliplatin had a mOS of ~11 months as measured from the start of gemcitabine therapy. Additionally, Conroy, *et al* reported the mOS in patients receiving second-line therapy in the FOLFIRINOX vs. gemcitabine trial⁽³⁾. In both arms, the mOS for second line therapy was 4.4 months. There are no prospective trials of FOLFIRINOX in patients whose disease had progressed on first line treatment, but a single-institution retrospective study of 27 patients treated with second-line FOLFIRINOX showed an ORR of 19 percent, and 12 others had stable disease (44%), and the median time to tumor progression was 5.4 months⁽³⁸⁾. Finally, the recently presented NAPOLI-1 Phase III trial demonstrated an improvement in overall survival of the combination of MM-398 plus 5-FU over 5-FU alone and it is anticipated this trial will lead to the first approved agent in the second line setting for metastatic pancreatic cancer⁽⁵⁵⁾. In the NAPOLI-1 trial, the median PFS for MM-398 plus 5FU was 3.1 months vs. 1.5 months for 5-FU alone.

1.5.3 Third Line Therapy in Pancreatic Cancer

Previous studies of third-line therapy in mPAC are limited but reveal stable disease in 25-31% of patients with no partial or complete responses (31% of patients in the GVAX/CRS-207 combination vaccine study had stable disease but only 52% of these patients were treated in the third-line setting)^(5, 6).

2.0 STUDY OBJECTIVES

2.1 Primary Objective:

2.1.1 Primary Objective of the Phase I Portion: To determine the Recommended Phase II dose (RP2D) of LEE011 in the combination with everolimus in patients with mPAC refractory to 5-FU- and GEM-based chemotherapy

2.1.2 Primary Objective of the Phase II Portion: To determine the progression-free survival (PFS) rate at 8 weeks (PFS_{8 weeks}) to assess the clinical efficacy of the combination of LEE011 and everolimus in patients with mPAC refractory to 5-FU- and GEM-based chemotherapy

2.2 Secondary Objectives

2.2.1 To determine the mPFS of patients treated with the combination of LEE011 and everolimus in patients with mPAC refractory to chemotherapy

2.2.2 To determine the mOS of patients treated with the combination of LEE011 and everolimus in patients with mPAC refractory to chemotherapy

2.2.3 To determine the best ORR, the largest percent decrease in tumor size from baseline as measured by expert radiologists using RECIST v1.1 criteria, defined as the proportion of patients with a CR or PR, of the combination of LEE011 and everolimus in patients with mPAC refractory to chemotherapy

2.2.4 To determine the safety and tolerability of the combination of LEE011 and everolimus in patients with mPAC refractory to chemotherapy

2.3 Exploratory Objectives:

2.3.1 To correlate the PFS_{8 weeks} to correlative scientific markers, including the analysis of tumor biopsies and blood-based markers, including RB, pRB, p16, cyclin D1, Ki67, MCM7, and pS6 levels by immunohistochemistry

2.3.2 To screen for use a targeted sequencing approach for genetic lesions observed in pancreatic cancer that includes KRAS, SMAD4, TP53, CDKN2A as well as other commonly mutated cancer genes

2.3.3 To assess blood for the analysis of circulating tumor DNA as a surrogate marker of disease burden. KRAS and other mutations will be used as the determinants of tumor selective DNA

2.4 Primary Endpoint:

PFS at 8 weeks in a patient with refractory mPAC treated with LEE011 and everolimus, defined as positive if a patient does not have evidence of PD at 8 weeks as measured by expert radiologists using RECIST v1.1 criteria

2.5 Secondary Endpoints:

2.5.1 PFS in a patient with refractory mPAC treated with LEE011 and everolimus, defined as the time from Cycle 1, Day 1 to PD (as measured by expert radiologists using RECIST v1.1 criteria), death from any cause, or last follow-up, as determined by the investigator

2.5.2 Overall survival (OS) in a patient with refractory mPAC treated with LEE011 and everolimus, defined as the time from Cycle 1, Day 1 to death from any cause or last follow-up

2.5.3 Best response in a patient, defined as the largest percent decrease in tumor size from baseline and categorized as a CR, PR, or SD by imaging studies, measured by expert radiologists using RECIST v1.1 criteria

2.5.4 Adverse events in a patient with refractory mPAC treated with LEE011 and everolimus, defined as the number of grade 3 and 4 toxicities according to National Cancer Institute Common Toxicity Criteria for Adverse Events (NCI CTCAE v4.03) that occur after Cycle 1, Day 1

2.6 Exploratory Endpoints:

2.6.1 Measurements of tumor cell proliferation, apoptosis, and RB-related gene expression by immunohistochemistry (IHC) in the pre-treatment and on-treatment biopsies:

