
	
Trial Auditing
 
The multi-institutional coordinator will arrange all primary source documents for the patients to be audited. This will include collecting copies of the primary source data for any patients treated at other sites.

Statistical Design, Feasibility, and Trial Duration
	
This is a multi-institutional single arm, open label Phase I/II study to evaluate the PFS_{8weeks} of the combination of LEE-011 plus everolimus, in patients with metastatic pancreatic cancer refractory to 5-fluorouracil (5-FU) and gemcitabine-based chemotherapy. Previous studies of third-line therapy in mPAC are limited but reveal stable disease in 25-31% of patients with no partial or complete responses (31% of patients in the GVAX/CRS-207 combination vaccine study had stable disease but only 52% of these patients were treated in the third-line setting)^(5, 6). It is hoped that the combination of LEE-011 plus everolimus can increase the PFS_{8weeks} to at least 50%, though early stopping rules are in place for lack of efficacy.
 
All patients meeting the eligibility criteria and who have signed a consent form, have begun treatment, are not lost to follow-up, and are not taken off study for reasons other than progression or death before 8 weeks will be considered evaluable for the assessment of the DCR.
 
Between 12 and 24 patients will be enrolled in the Phase I portion of the study, depending on whether DLTs occur and dose de-escalation is required. The 6 patients treated at the RP2D will be included in the Phase II portion of the study. We anticipate the combination will be well tolerated such that all of the patients in the Phase I portion are likely to be evaluable for the Phase II efficacy analysis.
 
26 evaluable patients will be enrolled in the Phase II portion of the study (though the potential drop-out rate is 10%), which will provide a 90% power to detect an improvement in the DCR from 25% (based on historical control) to 50%, assuming a 1-sided significance level of 0.1 and an accrual rate of 2 patients per month. A Simon's optimal two-stage design will be used to test the null hypothesis that the DCR $P \leq 0.25$ versus the alternative that $P > 0.5$. For the first stage, 11 patients will be entered to the study. The trial will be terminated if 2 or fewer patients achieve a PR, CR, or SD at 8 weeks. If at least 3 patients in the first stage achieve a PR, CR, or SD at 8 weeks, the trial goes on to the second stage. A total of 26 patients will be enrolled. If the total number of patients who achieve a PR, CR, or SD at 8 weeks is less than or equal to 9, the combination therapy will be rejected. If however, 10 or more patients achieve a PR, CR, or SD at 8 weeks the combination therapy will be considered for further analysis.
 
With 26 evaluable patients in the Phase II portion, combined with a minimum of 12 to a maximum of 18 patients enrolled strictly in the Phase I portion of the trial, there will be up to 44 patients enrolled. At an expected accrual rate of 3 patients per month, the expected accrual duration will be approximately 15 months.
 
Descriptive statistics will be used to summarize patients' demographics, toxicity, and quality of life. The PFS_{8weeks} will be estimated from the observed data with 95% exact binomial confidence interval. The nonparametric Kaplan-Meier method will be used to estimate the survival function and calculate the PFS and OS. The ORR will be estimated from the observed data with 95% exact binomial confidence intervals.

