3.4.3.3 Palliative radiotherapy

Palliative radiation is permitted if done solely for bone pain relief. It should not be delivered to a target lesion and it should not encompass more than 25% of irradiated bone marrow. No dose modification of study treatment is needed during palliative radiotherapy.

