7.4 Definition of Disease Progression

Disease progression will be defined as:

- 1) Radiologic progression of disease by RECIST v1.1 criteria.
- 2) Clinical progression as determined by the investigator, which may be characterized as, but is not limited to:
 - a. Increase of at least 2 points in ECOG performance status attributable to cancer progression.
 - b. Requirement for palliative radiation, chemotherapy or surgery.
- 3) Death from disease progression

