9.4 Endpoints

9.4.1 Primary Endpoint

PFS at 8 weeks is a complete response (CR), partial response (PR), or stable disease (SD) by imaging study (CT or MRI), evaluated by expert radiologists using RECIST v1.1 criteria, at the 8 week response assessment. Each patient will be categorized as either success/failure for being progression free at 8 weeks.

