9.5 Analysis Plan

9.5.1 Analytic plan for primary objective

The null hypothesis is that the PFS rate at 8 weeks is 25% (based on historical controls wherein third-line therapy in mPAC revealed stable disease in 25-31% of patients^{5,6}.) versus an alternative hypothesis that the rate is 50% or higher. The plan is to use a Simon's Minimax two-stage design with 11 patients enrolled during the first stage. If 3 or more (out of 11) patients are progression free the trial will continue with an additional 15 patients being enrolled during the second stage (for a total of 26 patients). If 10 or more patients are progression free at 8 weeks the trial will declare that the intervention has met the pre-specified criteria for success.

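### The 8-week primary endpoint is defined inconsistently, and no single rule classifies a patient who dies or progresses clinically before the scan

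*Combined protocol and SAP*

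**What the plan says.** **Success.** Section 2.4 states the primary endpoint as "defined as positive if a patient does not have evidence of PD at 8 weeks as measured by expert radiologists using RECIST v1.1 criteria". Section 9.4.1 says "PFS at 8 weeks is a complete response (CR), partial response (PR), or stable disease (SD) by imaging study (CT or MRI"), assessed at week 8, with each patient scored as success or failure. The futility counts in the synopsis (Study Design and Statistical Design rows) and Section 4.1.2, and the synopsis success count, also require PR, CR or SD at 8 weeks. Sections 9.2 and 9.5.1 say only that patients are progression-free.

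**Progression.** Besides RECIST progression, Section 7.4 lists "Clinical progression as determined by the investigator, which may be characterized as, but is not limited to" an ECOG rise of at least 2 points or "Requirement for palliative radiation, chemotherapy or surgery". It also lists death from disease progression. Death from another cause is not listed.

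**Denominator.** The synopsis Statistical Design row keeps patients who leave for progression or death before 8 weeks evaluable. The Study Design row allows up to 3 replacements for patients who leave before being evaluable, exempting only disease progression. Sections 4.1.2 and 9.2 replace only patients who were screened and did not start treatment within 3 weeks.

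**Death in secondary PFS.** Section 2.5.1 lists death from any cause with PD. Section 9.4.2.1 does the same, then censors patients who die on study.

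**Design.** Section 9.5.1: "The null hypothesis is that the PFS rate at 8 weeks is 25"%, against 50% or higher. The synopsis sets a one-sided alpha of 0.1 and uses another name for the quantity: "which will provide a 90% power to detect an improvement in the DCR from 25% (based on historical control) to 50"%.

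**The concern.** Section 2.4 defines success as the absence of a finding. Section 9.4.1 and the decision counts define it as the presence of one. The two agree for a patient who has an evaluable 8-week scan and differ for a patient who never reaches it. Section 7.4 brings in a third notion, clinical progression, which neither imaging definition uses.

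Such patients are foreseeable. Section 4.4.9.1 withdraws patients for clinical progression, and Section 7.3 provides for symptomatic deterioration without objective progression. The trial is single-arm and open-label with small counts, so the rule for these patients should be fixed before outcomes are seen. Otherwise the choice of section can decide the interim or the final result.

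**Working it through.** **1. The definitions side by side**

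| Patient before or at week 8 | Section 2.4, read literally | Section 9.4.1 and the CR/PR/SD counts | Section 7.4 |
|---|---|---|---|
| Dies of progression, no scan | positive | not a success | progressed |
| Dies of another cause, no scan | positive | not a success | not listed |
| Clinical progression, no scan | positive | not a success | progressed |
| Clinical progression, SD on the 8-week scan | positive | success | progressed |

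In the first three rows Section 2.4 differs from Section 9.4.1. In the fourth those two agree, and the conflict is with Section 7.4. The second row has a further problem: the synopsis evaluability rule keeps the patient in the denominator, while its replacement rule on its face would allow replacement.

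**2. The plan's own design**

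Inputs (Section 9.5.1 and the synopsis): 11 patients in stage 1, continue with 3 or more; 15 further patients, success with 10 or more of 26; rates 25% and 50%; one-sided alpha 0.10; power 90%.

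P(success | p) = Σ (x = 3 to 11) C(11,x) pˣ (1−p)¹¹⁻ˣ × P[Bin(15,p) ≥ 10−x]

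- p = 0.25: 0.0857, within the 0.10 limit. The probability of stopping at stage 1 is 0.455.
- p = 0.50: 0.9005.

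The stated design reproduces, so the fault is not in the sample size.

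**3. Sensitivity to classification**

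Let e be the share of patients who die or progress clinically before the scan without radiologic PD. The documents give no value for e, so a range is assumed. One of 26 is 3.8% and two of 26 are 7.7%. The true success rate is held at 25%.

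- Scored positive under a literal Section 2.4: apparent rate p = 0.25 + e.
- Replaced: apparent rate p = 0.25 / (1 − e).

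| e | p if scored positive | P(false success) | p if replaced | P(false success) |
|---|---|---|---|---|
| 0 | 0.25 | 0.0857 | 0.25 | 0.0857 |
| 4% | 0.29 | 0.1860 | 0.2604 | 0.1073 |
| 8% | 0.33 | 0.3278 | 0.2717 | 0.1345 |
| 10% | 0.35 | 0.4088 | 0.2778 | 0.1505 |

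The replacement column takes every such patient as replaced. The synopsis limits replacements to 3 and exempts disease progression, so this is an upper illustration for a given e.

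If all these patients are failures and stay in the denominator, the stated 0.0857 and 0.9005 stand.

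**The case against.** The best defence is that the operative rules already settle the main case. The decision counts require a CR, PR or SD, Section 9.4.1 makes the outcome binary, and the synopsis keeps early deaths evaluable. A patient who dies unscanned at week 5 is then an evaluable non-success. Applied strictly, the evaluability rule would also block replacement, since that patient is already evaluable. Section 2.4 itself presupposes a radiologist's reading. A reader might infer that it declares a death a success, but it is silent on death, and Section 2.5.1 just below names death from any cause. Response evaluation at the final visit (Sections 4.4.8 and 4.4.9.2) and the effort in Section 7.3 to document objective progression should also reduce the number of unscanned progressors.

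Most of this stands. The CR/PR/SD reading is the likelier one, and a positive score for an early death follows only from the literal wording of Section 2.4. Three things remain:

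- The endpoint's name does not settle how deaths count, because Section 9.4.2.1 censors on-study deaths for secondary PFS.
- A clinical progressor with an SD scan is a success under both imaging definitions and has progressed under Section 7.4.
- The synopsis replacement rule names only disease progression as its exemption, and it disagrees with Sections 4.1.2 and 9.2.

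**Conclusion.** The inconsistency is real and affects the count on which both Phase II decisions rest. One reclassified patient can change 2 to 3 of 11, or 9 to 10 of 26.

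The figures of 0.19–0.41 (scored positive) and 0.11–0.15 (replaced) rest on an assumed share of 4–10% and a true rate of 25%. A reader might take the larger range as the trial's expected false-positive rate. The documents do not support that: it applies only if the literal Section 2.4 wording overrides the CR/PR/SD counts, and no rate of early death or clinical decline is given.

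A reader might also infer that any need for palliative radiation is automatically progression. Section 7.4 offers it as an example under the investigator's judgement.

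**What to change.** Use one definition in Sections 2.4, 9.2, 9.4.1 and 9.5.1 and in the synopsis: success means alive with CR, PR or SD on the 8-week scan, and no progression (RECIST, or clinical as in Section 7.4) or death on or before it.

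State that any treated patient who dies from any cause or progresses before the assessment is a failure, stays in the denominator and is not replaced. Amend the synopsis replacement rule to say so and make it agree with Sections 4.1.2 and 9.2.

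Patients with no scan for other reasons should follow one reconciled evaluability and replacement rule, with a sensitivity analysis counting them as failures. Counting them as failures in the primary analysis would override the present evaluability rule and cost power. With the plan's 10% dropout, taken as independent of outcome and not replaced, 0.50 × 0.90 = 0.45 and power falls from 0.90 to 0.79.

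Separately, Section 3.4.3.3 says "Palliative radiation is permitted if done solely for bone pain relief", Section 4.4.9.1 withdraws a patient who requires radiotherapy, and Section 7.4 gives palliative radiation as an example of clinical progression. These passages must be reconciled, since Section 7.4 would feed the endpoint.

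The cost is a protocol amendment to wording, with no added patients. The observed rate may be slightly lower.
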